# **Duration of Clinical Investigation**

Each subject, and therefore use of the device, is expected to take 1.5-2 hours. Data collection will occur over a 3-5 day period for this study population.

# **Criteria for Study Termination**

The study will be terminated if any of the following conditions occurs:

- Study is complete
- Unable to obtain vascular access
- Initial blood draw values of, COHb >3%, MetHb > 2%, and tHb <10g/dl (Note: COHb may be lowered through an exercise of hyperventilation and elevated levels of oxygen being administered to the subject.)
- Subject withdrew consent. The subject may stop the study for any reason without prejudice
- Withdrawal by Sub-Investigator / Investigator. The clinician or gas controller may terminate the study at his/her discretion
- Study Stopped due to Technical Problems
- Study may be stopped due to Protocol Deviation
- Study Terminated by Sponsor
- Study Stopped due to Adverse Event
- Development of any cardiac arrhythmia, except sinus arrhythmia <120 bpm
- Development of clinically significant ST or T segment changes in the ECG

Clinimark, LLC	TITLE: BORA Band SpO2 Validation Study	DOCUMENT NUMBER	REV
[name]	Study ID# PR 2018-312	PR# 2018-312	1
[name], USA	Principal Investigator: [name] Site ID # 001	Page 19 of 36	1

- Sustained sinus tachycardia ≥120 bpm
- Onset of PVCs
- Sustained levels lower than the target SpO2. The lowest target is 70% SpO2. Due to unpredictable human physiology, the subject may drift below 67%. Should this occur, an attempt will be made to increase the oxygen saturation level by increasing the FiO2 level to achieve an SpO2 in the 67-73% range or a decision is made to increase the FiO2 to a new SpO2 range or terminate the study.

Any data collected to the point of a decision to terminate the study will be reviewed for inclusion to the analysis prior to generation of the final results. Data excluded from the analysis will be documented with justifications.

# **Procedure**

- 1. Complete Equipment checkout list prior to starting study. Calibrate / check FiO2 monitor(s).
- Set the clocks to sync data collection between the Sponsor and Clinimark systems.
- 3. Explain the procedure to the subject. Have them read the Informed Consent Form, and review the information answering all questions. Once all questions have been answered, have the subject sign the form. Have the subject complete the Health Assessment Form and verbally question the subject about their health history. Each subject will be asked if they want a copy of the consent form prior to release.
- 4. Apply Finger sensor to thumb of hand where the arterial line will be placed. Record perfusion index (PI) value from 3900 TT+ Pulse Oximeter. Perform a modified Allen's test to ensure sufficient blood flow to the hands. Occlude both radial and ulnar arteries until there is no plethysmographic waveform and the PI is essentially zero. Release the ulnar artery holding the radial artery firm. Record the PI level. The ratio of the ulnar artery PI measurement to the starting PI level should be greater than or equal to 0.4 to qualify for the study. This is a safeguard to ensure there is a sufficient blood flow supply to the hand should the flow from the radial artery become altered.
- 5. Take subject's blood pressure and record values.
- 6. Apply ECG leads to the subject, review for normal sinus rhythm.
- 7. Based on the responses to the Health assessment form, record accepted or declined from the study. Continue if accepted into the study.
- 8. A qualified clinician will use local anesthesia and with the assistance of ultrasound, place the arterial catheter in the radial artery of the non-dominate (preferred) hand. The arterial line is then secured with tape to the subject's arm.
- 9. Setup and verify communication between the devices and data collection system.
- 10. Record device information for tracking. (manufacturer, model #, serial or lot, hardware / software control info).
- 11. Record subject information. Subject number and demographics information for subject description.
- 12. Have subjects recline.
- 13. Apply sensors to the subject. Shield any adjacent sensors to prevent optical cross-talk.
- 14. Adjust sensors as appropriate and record on test form.
- 15. A hot water bottle may be placed on each arm to improve the perfusion and facilitate the blood draws.
- 16. Allow readings to stabilize. Record baseline SpO2 and Pulse rate on the test form.

Clinimark, LLC	TITLE: BORA Band SpO2 Validation Study	DOCUMENT NUMBER	REV
[name]	Study ID# PR 2018-312	PR# 2018-312	1
[name], USA	Principal Investigator: [name] Site ID # 001	Page 20 of 36	

[figure not shown]

- 17. Begin program to start gas flow. Verify that FiO2 is at appropriate starting level (typically 18-21%) prior to connecting subject to breathing circuit.
- 18. Connect the subject to the breathing circuit and adjust the gas flow delivery for subject comfort.
- 19. Start data collection.
- 20. The program will be run in manual mode. Gas mixture changes will be set by the controller. The gas mixture will be delivered to induce hypoxia in a stair stepped manner. Data collection will be evenly distributed by decade over the oxygen saturation range.
- 21. The clinician monitors and records the following information periodically. SpO2, pulse rate, EtCO2, respiration rate, relevant information on the ECG rhythm, FiO2. The clinician will monitor the arterial line and subject's well-being throughout the test confirming that the subject is doing "ok". Subject will be advised during the study that he/she may stop the test at any time.
- 22. While breathing room air mixtures, collect baseline arterial samples and measure on the CO-Oximeter. The method for sampling will be:
  - Mark data for start of stability period hold 30 seconds to 1 minute
  - Draw waste or leader blood sample prior to draw, mark data
  - Draw arterial blood sample marking data
  - Wait approximately 15 to 30 seconds, draw waste or leader blood sample prior to draw
  - Draw additional arterial blood sample marking data
  - · Change to next gas level

Note timing may vary based on the subject's stability.

- 23. Should the initial COHb reading be out of range (>3%) as measured by Reference CO-Oximetry, then a determination will be made as to the viability of blowing off the COHb levels through an exercise of hyperventilation and elevated levels of oxygen being administered to the subject. If this is the case, blood samples will be drawn to monitor the COHb level until it is acceptable or a determination is made to withdraw the subject.
- 24. Multiple plateaus will be achieved throughout the range from 100% to 70%.
- 25. The clinician monitors and records the following information periodically. SpO2, pulse rate, EtCO2, respiration rate, relevant information on the ECG rhythm, FiO2. The clinician will monitor the subject's wellbeing throughout the test confirming that the subject is doing ok.
- Subject will be advised during the study that he/she may stop the test at any time.
- 27. The gas controller monitors the gas delivery and data collection system to ensure proper functionality. Performance of the test devices may be noted on the form as well.
  - The test may be stopped at any time by the subject, the clinician, the gas controller. The test will also be stopped if the SpO2 level goes below the minimum SpO2 or the FiO2 goes below 9%.
- 28. Arterial blood sampling will be repeated at each stable plateau. Method used will be same as described in step #22 above.

Goal is to collect 20-30 data points per subject with an equal distribution of data by decade across all subjects. The stable plateaus will allow for data to be collected in the following ranges 95-100, 90-95, 85-90, 80-85, 75-80, 67-75. In general, 4 to 8 discrete points will be collected at each of the levels such that the overall data of the population is evenly distributed by decade and the minimum number of points is met for the data analysis. A fewer number of data points are expected on some subjects that are unable to tolerate the duration of the lower hypoxic levels.

- 29. During the course of the study, the subject may be re-saturated to above 80% SpO2 for a recovery period. The subject then may reattempt the lower SpO2 levels.
- 30. Once the lowest level SpO2 has been achieved and data collection has been completed, the subject will be given a gas mixture returning him/her to baseline levels.
- 31. The breathing circuit is disconnected and the subject is monitored for a few minutes to ensure he/she maintains normal baseline levels.
- 32. All equipment will be removed from the subject.
- 33. The arterial line will be removed and a pressure bandage will be applied to the subject for approximately 15 minutes or until bleeding has stopped.
- 34. The clinician will review any final questions with the subject and ask if there were any effects from the study. The subject will be given final instructions for care of the wrist which had the arterial line. The subject will be provided with phone numbers for questions pertaining to participation in this study or research-related injury or reaction post the study. The subject will be informed of the follow up procedure post the study.

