# **Design of the Clinical Investigation**

#### Method

This study is a comparative, single-center, non-randomized study with a minimum of 10 subjects. Each subject test is expected to take approximately 1.5 to 2 hours. The overall data collection process will occur over a 3-5 day period for this study population.

Subjects will be provided an IRB approved Informed Consent which covers the essential information in the protocol, ISO 14155 (as reference only) and applicable regulatory requirements for a non-significant risk medical device investigation. Subjects will be provided sufficient time to review the informed consent and have all questions answered regarding their participation before enrollment or conduct of study specific procedures. As applicable, subjects will be told about any new information that might change their decision to participate.

Subjects who have completed (signed and dated) the informed consent and health questionnaire form and meet inclusion criteria and none of the exclusion criteria will be enrolled in the study. If the Informed Consent Form (ICF) is amended/updated throughout the life-cycle of the study, a determination will be made as to whether the subjects who have completed the study need to reconsent by reviewing, signing and personally dating the updated ICF.

Clinimark, LLC	TITLE: BORA
[name]	Study ID# PR 20:
[name], USA	Principal Investig

REV

1

Qualified healthy volunteers will be enrolled into the study. Subjects will recline for the study. Reference sensor(s) will be placed on each subject to evaluate the SpO2 accuracy and performance. Shield material may be used between any adjacent finger sensors to prevent optical crosstalk.

Simultaneous data collection will be set up for device under test and the control pulse oximeter. The data from the test device will be collected by the sponsor or trained Clinimark Study staff. Data will be collected for 1 second intervals data analysis. The SpO2 accuracy of the test devices will be evaluated over the oxygen saturation range between 70-100%.

The investigational device will only be placed on the wrist. The control pulse oximeter may be alternated through fingers between subjects.

A photo or video may be recorded to document the study if acceptable with the subject. Photo or video may be used for internal purposes, such as training by the sponsor.

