# **Data Collection Forms / Case Report Forms**

To ensure the quality and integrity of the data, it is the responsibility of the Investigator(s) or designee to complete the Case Report Forms (CRFs) for each subject who is enrolled to participate in this study. In some cases the data collection forms will also be the source document for some information that is not directly collected in the Health Assessment Form. The following information will be recorded on the site's data collection forms (CRF):

- Study date, Subject ID#, Subject Initials, and Relevant Subject Demographics, Associated Electronic Filename(s)
- Evidence that informed consent was signed and dated prior to the subject participating in the study
- Information for Subject Inclusion or Exclusion to the study
- Equipment calibration and communication check out
- Device usage / sensor placement on the subject
- Baseline SpO2 and pulse rate
- Annotations on data point markers, stability, and other observations used in the data analysis
- Protocol deviation reporting (only if needed)
- Adverse Events reporting (only if needed)

Clinimark, LLC	TITLE: BORA Band SpO2 Validation Study	DOCUMENT NUMBER	REV
[name]	Study ID# PR 2018-312	PR# 2018-312	1
[name], USA	Principal Investigator: [name] Site ID # 001	Page 27 of 36	

- Study termination
- · Subject Follow up form

A black or blue pen will be used to record data on the data collection forms. Recorded information should be legible and completed. Erroneous entries should be crossed out, corrected with the change, initialed and dated by the individual making the correction. The Investigator(s) or designee will sign and date at indicated places on each page of the data collection form. The Protocol Deviations Reporting can be signed and dated by the designee only if there are no deviations, otherwise the Sub-Investigator or Investigator should review, sign and date. The Adverse Events Reporting should be signed and dated by the designee and a Sub-Investigator or Investigator. The Principal Investigator needs to review, sign and date all serious adverse events. The Investigator or designee will provide a final signature indicating that a thorough inspection of all subject data has been performed and will thereby certify the contents of the forms. The Investigator's Certification Statement will disclose the overall documentation, study oversight and certification of the study.

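### Staff who set plateaus, time draws and annotate points are not masked from the test band, so draws timed on band-control agreement are not prevented

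*Combined protocol and SAP*

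**What the plan says.** - **Intended basis.** Control Oximetry System and Statistical Analysis assign plateau targeting and stability to the control oximeter. Control oximeter stability criteria removes a point if the control varies by more than 2% during the draw, or by more than 3% over the review period.
- **Gas.** Procedure step 20 runs in manual mode: "Gas mixture changes will be set by the controller".
- **Timing.** Step 22 sets the sequence: mark the start of stability, hold 30 seconds to 1 minute, draw, wait about 15 to 30 seconds, draw again, change level. It adds: "Note timing may vary based on the subject's stability". Step 28 repeats this at every plateau.
- **Sight of the band.** Step 27 reads "The gas controller monitors the gas delivery and data collection system to ensure proper functionality", followed directly by "Performance of the test devices may be noted on the form as well".
- **Handling of band data.** Data Acquisition System for the Investigational Device assigns collection to the sponsor, on a separate system. The Method section says "The data from the test device will be collected by the sponsor or trained Clinimark Study staff".
- **Annotations.** The case report form records "Annotations on data point markers, stability, and other observations used in the data analysis".
- **Sensors.** Step 14: "Adjust sensors as appropriate and record on test form".
- **Decision rule.** Pass / Fail Criteria: pooled A_RMS over 70-100% of at most 3.5, as a point estimate.

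No section says that the band's reading is hidden from anyone.

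**The concern.** The staff who decide that a plateau is good enough to sample should not know whether the device under test currently agrees with the control. If they can see it, waiting until the two agree is an easy and possibly unconscious habit. A_RMS is built from squared errors, so avoiding a small number of large errors moves it more than their count suggests, and selection on agreement can only lower it. The pass rule has no confidence margin to absorb such a shift.

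The planned checks act on draws that were taken. The stability rules remove unstable points, and the exclusion rationale explains removed points. Nothing requires a draw once the control is stable, limits the wait, or calls for a list of marked stability periods that produced no sample.

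**Working it through.** **1. The plan's own figure.** 10 subjects x 20 points = 200, the stated minimum (15 x 30 = 450 at most). The documents give no expected A_RMS, error SD or control-oximeter error, so every input below other than 200 and 3.5 is an assumption.

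**2. Inputs.** The band error is normal with mean 0 and true A_RMS 3.8, a device that should fail. Between-subject SD is 2.0, so within-subject SD = sqrt(3.8² - 2.0²) = sqrt(10.44) = 3.23. Control-oximeter error has SD 1.5. SaO2 is not known at the moment of the draw, so staff could see only the gap between band and control. Its variance is 14.44 + 2.25 = 16.69, SD 4.09.

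**3. Draws lost outright.** If draws avoid the share p of moments with the largest gap:

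A_RMS shown = true x sqrt(1 - r x d), where r = 14.44 / 16.69 = 0.865 and d = 2zφ(z) / (1 - p).

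For p = 5%, z = 1.96, so gaps above 1.96 x 4.09 = 8.0 points are avoided, about 10 of 200 draws. Then d = 2 x 1.96 x 0.0584 / 0.95 = 0.241, and A_RMS shown = 3.8 x sqrt(1 - 0.865 x 0.241) = 3.8 x 0.890 = **3.38**.

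The same formula gives 3.59 for p = 2% (about 4 of 200 draws) and 3.12 for p = 10%. For a true A_RMS of 4.0 the three values are 3.77, 3.55 and 3.27. Simulation agrees. With 10 subjects x 20 points, the chance that a true-3.8 device passes rises from about 16% to about 74% in the 5% case.

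**4. Draws deferred and retaken.** Waiting cannot remove a subject's fixed offset, or error that stays constant on the plateau. I simulated 2 million draws with the same inputs. A draw whose gap exceeded 8.0 points was retaken up to five times, and only the time-varying part of the within-subject error was redrawn.

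| Share of within-subject variance that changes over time | A_RMS shown (true 3.8, 5% threshold) |
|---|---|
| 0% | 3.80 |
| 10% | 3.70 |
| 30% | 3.57 |
| 50% | 3.48 |
| 100% | 3.39 |

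The lost-outright figure is approached only when nearly all within-subject error refreshes between moments. For a true 4.0, the 10% and 30% rows give about 3.9 and 3.75, both still failing.

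**5. No selection.** If draws are timed without regard to the band, A_RMS shown = true A_RMS and the bias is zero.

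**The case against.** The strongest case is that the plan already says what governs a draw. Timing varies with the subject's stability, stability is judged on the control oximeter with numerical limits, and the step 22 sequence is set out in order. No text makes the band's reading a reason to wait. This stands, and it means that the plan followed as intended gives no bias.

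Four further points also stand:

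- A reader might infer from step 27 that the gas controller watches the band's SpO2. The sentence is passive, names no observer and may mean only dropouts or lost connection. A live SpO2 is not assured either: the device description lists ratio of ratios and/or SpO2.
- A reader might infer from step 14 that the band can be repositioned mid-run because it disagrees with the control. That step precedes baseline (step 16) and the start of data collection (step 19), and the adjustment is recorded.
- A reader might infer that deferral leaves no trace. Marked stability periods, 1-second data, synchronised clocks and preserved original files would let a marked hold without a draw be reconstructed. Only a draw put off before the mark would be invisible.
- Losing a few draws would not usually turn a fail into a pass: at 2%, a true 3.8 still shows 3.59.

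What the objection does not answer is the absence of masking. The stability limits remove samples already drawn. They do not oblige a draw when the control is stable, and reconstruction from raw files is possible but not planned. The separate sponsor system gives no assurance while the Method section also allows site staff to collect band data.

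**Conclusion.** The concern holds as a gap in conduct safeguards. The plan relies on the control oximeter for plateaus and stability but does not mask the band from those who set gas levels, accept plateaus, time draws or annotate points. Selective timing is therefore not prevented and, before a stability mark, not detectable.

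The documents do not support the stronger reading that draws will be timed on the band or that A_RMS will come out too low. Any bias would favour a pass, but its size is unknown. On the assumptions above, a true 3.8 would show about 3.4 if the worst 5% of draws were lost, and about 3.7 to 3.5 if they were retaken with 10 to 50% of within-subject variance changing over time. Nothing in the documents fixes that share, the SDs, or how often anyone would act on the band. The case for change rests on the cheapness of the safeguard and a pass rule without margin.

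**What to change.** - **Step 27:** limit the note on test devices to connection or signal status.
- **Masking:** state that the band's SpO2 is hidden from the gas controller, the clinician and anyone accepting plateaus, timing draws or annotating points until the subject's session is closed.
- **Trigger:** state that draws are triggered by control-oximeter stability only.
- **Log:** list every marked stability period not followed by a draw, with the reason.
- **Repositioning:** once data collection has started, allow the band to be moved only for lost contact or no signal, and log it.
- **Responsibility:** reconcile Data Acquisition System for the Investigational Device with the Method section on who collects band data.

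The cost is a masked screen on the sponsor's application and a few lines of procedure. The small downside is that site staff would see signal loss on the band but not implausible values. Subject monitoring is unaffected, because the plan already assigns it to the control oximeter and the safety monitor.

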# Statistical Analysis

The purpose of this clinical study is to validate the SpO₂ accuracy of the BiOSENCY BORA BAND™ wristband Pulse Oximeter during non-motion conditions over the range of 70-100% SaO₂ as compared to arterial blood samples assessed by CO-Oximetry. Data analysis may occur in the following manner:

Data analysis will follow ISO80601-2-61:2017, Annex EE and the FDA Guidance Document for Pulse Oximeters (March 4, 2013). The reference guidance documents clearly define the study, number of subjects, data points needed for the analysis and handling of missing data or data that is removed from the analysis. This is achieved through a minimum of 200 paired observations of Test and Reference values equally distributed over the specified  $SpO_2$  accuracy range (70-100%) of the device under test.

Clinimark, LLC	TITLE: BORA Band SpO2 Validation Study	DOCUMENT NUMBER	REV
[name]	Study ID# PR 2018-312	PR# 2018-312	1
[name], USA	Principal Investigator: [name] Site ID # 001	Page 22 of 36	) <del>-</del>

The data will be collected on a minimum of 10 healthy adult volunteer subjects who range in age, gender and skin tone with 2 of the subjects or 15% of the subject pool (whichever is larger) having deep skin pigmentation tones. An Accuracy Root Mean Square ( $A_{RMS}$ ) calculation is used as a means to define the SpO2 Accuracy. The controls of the study will be provided in the following manner. The control oximeter will provide the real time oxygen saturation level of the subject for determination of plateau levels and safety. Additionally, the oxygen saturation values (SpO2) of a control oximeter will be used to assess the stability of the plateaus for data collection. There are no provisions for an interim analysis. For the validation, the SpO2 accuracy of test pulse oximetry system is compared to the Gold Standard measurement of blood SaO2 by a CO-Oximeter. Data analysis & demographics will be presented in the final report.

